11.1.6 Progression-Free Survival

Overall Survival: Overall Survival (OS) is defined as the time from randomization (or registration) to death due to any cause, or censored at date last known alive.

Progression-Free Survival: Progression-Free Survival (PFS) is defined as the time from randomization (or registration) to the earlier of progression or death due to any cause. Participants alive without disease progression are censored at date of last disease evaluation.

Time to Progression: Time to Progression (TTP) is defined as the time from randomization (or registration) to progression, or censored at date of last disease evaluation for those without progression reported.

11.1.7 Response Review

Independent, central review of the radiology assessment will be performed by through the Dana Farber Harvard Cancer Center Tumor Imaging Metrics Core (TIMC).

12. DATA REPORTING / REGULATORY REQUIREMENTS

Adverse event lists, guidelines, and instructions for AE reporting can be found in Section 7 (Adverse Events: List and Reporting Requirements).

12.1 Data Reporting

12.1.1 Method

The ODQ will collect, manage, and perform quality checks on the data for this study.

Note: If your study has been assigned to CDUS-Complete reporting, **all** adverse events (both routine and expedited) that have occurred on the study and meet the mandatory CDUS reporting guidelines must be reported via the monitoring method identified above. If your study has been assigned to CDUS-Abbreviated reporting, no adverse event reporting (routine or expedited) is required to be reported via CDUS.

12.1.2 Responsibility for Data Submission

Investigative sites within DF/HCC or DF/PCC are responsible for submitting data and/or data forms to the ODQ according to the schedule set by the ODQ.

For CDUS and CMTS submissions:

Participant institutions are responsible for submitting CDUS data and/or data forms to either the Coordinating Center or to the Lead Organization on the study quarterly. The date for submission to the Coordinating Center or to the Lead Organization will be set by them. CDUS does not accept data submissions from the participant institutions on the study. When setting the dates, allow time for Coordinating Center compilation, Overall PI review, and timely submission to CTEP by the quarterly deadlines. For trials monitored by CTMS, a quarterly report of data will be provided by Theradex to the Coordinating Center.

Either the Coordinating Center or the Lead Organization is responsible for compiling and submitting CDUS data to CTEP for all participant institutions and for providing the data to the Overall PI for review.

12.2 Data Safety Monitoring

The DF/HCC Data and Safety Monitoring Committee (DSMC) will review and monitor toxicity and accrual data from this study. The committee is composed of clinical specialists with experience in oncology and who have no direct relationship with the

study. Information that raises any questions about participant safety will be addressed with the Overall PI and study team.

The DSMC will review each protocol up to four times a year or more often if required to review toxicity and accrual data. Information to be provided to the committee may include: up-to-date participant accrual; current dose level information; DLT information; all grade 2 or higher unexpected adverse events that have been reported; summary of all deaths occurring with 30 days of intervention for Phase I or II protocols; for gene therapy protocols, summary of all deaths while being treated and during active follow-up; any response information; audit results, and a summary provided by the study team. Other information (e.g. scans, laboratory values) will be provided upon request.

12.3 Regulatory Considerations

12.3.1 Protocol Review and Amendments

This protocol, the proposed informed consent and all forms of participant information related to the study (e.g., advertisements used to recruit participants) and any other necessary documents must be submitted, reviewed and approved by a properly constituted IRB governing each study location.

Any changes made to the protocol must be agreed upon by the DFHCC Overall Principal Investigator, shall be submitted as amendments, and must be approved by the IRB prior to implementation. Any changes in study conduct must be reported to the IRB. The DF/HCC Overall Principal Investigator (or Protocol Chair) will disseminate protocol amendment information to all participating investigators.

All decisions of the IRB concerning the conduct of the study must be made in writing.

12.3.2 Informed Consent

All participants must be provided a consent form describing this study and providing sufficient information for participants to make an informed decision about their participation in this study. The formal consent of a participant, using the IRB approved consent form, must be obtained before the participant is involved in any study-related procedure. The consent form must be signed and dated by the participant or the participant's legally authorized representative, and by the person obtaining the consent. The participant must be given a copy of the signed and dated consent document. The original signed copy of the consent document must be retained in the medical record or research file.

12.3.3 Ethics and Good Clinical Practice (GCP)

This study is to be conducted according to the following considerations, which represent good and sound research practice:

- E6 Good Clinical Practice: Consolidated Guidance
www.fda.gov/downloads/RegulatoryInformation/Guidances/UCM129515.pdf
- US Code of Federal Regulations (CFR) governing clinical study conduct and ethical principles that have their origin in the Declaration of Helsinki
 - Title 21 Part 11 – Electronic Records; Electronic Signatures
www.access.gpo.gov/nara/cfr/waisidx_02/21cfr11_02.html
 - Title 21 Part 50 – Protection of Human Subjects
www.access.gpo.gov/nara/cfr/waisidx_02/21cfr50_02.html
 - Title 21 Part 54 – Financial Disclosure by Clinical Investigators
www.access.gpo.gov/nara/cfr/waisidx_02/21cfr54_02.html
 - Title 21 Part 56 – Institutional Review Boards
www.access.gpo.gov/nara/cfr/waisidx_02/21cfr56_02.html
 - Title 21 Part 312 – Investigational New Drug Application
www.access.gpo.gov/nara/cfr/waisidx_02/21cfr312_02.html
- State laws
- DF/HCC research policies and procedures
<http://www.dfhcc.harvard.edu/clinical-research-support/clinical-research-unit-cru/policies-and-procedures/>

It is understood that deviations from the protocol should be avoided, except when necessary to eliminate an immediate hazard to a research participant. In such case, the deviation must be reported to the IRB according to the local reporting policy.

12.4 Study Documentation

The investigator must prepare and maintain adequate and accurate case histories designed to record all observations and other data pertinent to the study for each research participant. This information enables the study to be fully documented and the study data to be subsequently verified.

Original source documents supporting entries in the case report forms include but are not limited to hospital records, clinical charts, laboratory and pharmacy records, recorded data from automated instruments, microfiches, photographic negatives, microfilm or magnetic media, and/or x-rays.

12.5 Records Retention

All study-related documents must be retained for the maximum period required by applicable federal regulations and guidelines or institutional policies.

13. STATISTICAL CONSIDERATIONS

This is a phase II trial to assess the effect of adding an abbreviated MAPK-targeted therapy to pembrolizumab in patients with unresectable or metastatic melanoma. Two cohorts of patients will be enrolled and analyzed separately: Patients with BRAF^{V600} mutant melanoma, and patients with BRAF^{V600} wild-type melanoma. The trial will be based on parallel Simon two-stage designs according to disease cohort and will provide preliminary estimates of toxicity and efficacy.

13.1 Study Design/Endpoints

Primary Endpoint: The rate of clinical benefit (CBR), defined as the proportion of patients who have CR/PR/SD at the week-24 scan while remaining off MAPK-targeted therapy (MTT) after induction. To be evaluable for the primary endpoint, patients must receive at least one dose of pembrolizumab, any patient who is unevaluable for response will be classified as a non-responder.

Secondary Endpoints:

13.1.1 Overall Survival (OS): The time between the first dose of targeted therapy and death from any cause. For patients who are lost to follow-up or who have no documentation of death at the time of final analysis, follow-up will be censored at the date of last assessment of vital status.

13.1.2 Safety and tolerability: Safety and toxicity will be monitored throughout the study. An early, comprehensive safety review will be conducted at the end of the first-stage of the Simon two-stage design to review the data for unexpected severe toxicities due to the drug combination.

13.1.3 Describe temporal changes in the tumor microenvironment as a function of therapy.

Design: For each disease cohort, the Simon two-stage design is based on a type-I error rate of 0.1, at least 85% power, and a total sample size of 25 subjects. A complete safety assessment is planned to coincide with the review of clinical benefit at the end of the first stage.

Within cohort, the null hypothesis of a true CBR of 0.50 will be tested against a one-

sided alternative CBR of 0.75. The benchmark CBR rate of 0.50 is based on the results of the Keynote 001 trial in patients with refractory or first-line malignant melanoma treated with pembrolizumab (Robert, ASCO 2016) that reported a CBR of 0.51 regardless of BRAF mutation status. A short course of MAPK-targeted therapy in addition to pembrolizumab would be considered worthy of further investigation if there is evidence of an improvement in CBR to 0.75. Fourteen (14) subjects that are evaluable for the primary endpoint (defined as receiving at least 1 dose of dabrafenib/trametinib/pembrolizumab combination therapy prior to treatment discontinuation for any reason.) will be enrolled in the first stage. If 8 or fewer subjects with clinical benefit are observed, enrollment will stop. If there are 9 or more subjects with clinical benefit, then an additional 11 subjects will be enrolled for a total of 25. The null hypothesis will be rejected if 16 or more subjects with clinical benefit are observed in 25 subjects. This design yields power of 86% (target type II error of 0.15) when the CBR rate is 0.75. If the null hypothesis is true, the probability is 0.79 that enrollment to a cohort will stop at the end of the first stage. This high probability of stopping under the null was chosen to require strong evidence of benefit before opening the second stage.

13.2 Sample Size, Accrual Rate and Study Duration

The total sample size for this study is 50 patients (25 patients per cohort). At an anticipated accrual rate of 2 patients per month, enrollment is expected to be completed in approximately two years.

13.3 Analysis of Primary Endpoints

Clinical benefit rates will be presented for each cohort with 90% confidence intervals based on the method of Atkinson and Brown, which allows for the two-stage design. For samples of size 25, each confidence interval will be no wider than 0.35.

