For both cohorts, the null hypothesis of a true CBR of 0.50 will be tested against a one-sided alternative CBR of 0.75. The benchmark CBR rate of 0.50 is based on the results of the Keynote 001 trial in patients with refractory or first-line malignant melanoma treated with pembrolizumab (Robert, ASCO 2016) that reported a CBR of 0.51 regardless of BRAF mutation status. A short course of MAPK-targeted therapy in addition to pembrolizumab would be considered worthy of further investigation if there is evidence of an improvement in CBR to 0.75. Fourteen (14) subjects that are evaluable for the primary endpoint (defined as receiving at least 1 dose of dabrafenib/trametinib/pembrolizumab combination therapy prior to treatment discontinuation for any reason.) will be enrolled in the first stage, and if 8 or fewer subjects with clinical benefit are observed, then enrollment will stop. If there are 9 or more subjects with clinical benefit, then an additional 11 subjects will be enrolled, for a total of 25. The null hypothesis will be rejected if a total of 16 or more subjects with clinical benefit are observed in 25 subjects. This design yields power of 86% (target type II error of 0.15) when the CBR rate is 0.75. If the null hypothesis is true, the probability is 0.79 that enrollment to a cohort will stop at the end of the first stage. This high probability of stopping under the null was chosen to require strong evidence of benefit before opening the second stage.

Clinical benefit rates will be presented with 90% confidence intervals based on the method of Atkinson and Brown, which allows for the two-stage design.

All reported adverse events will be summarized as part of the early safety review at the

CONFIDENTIAL

This document is confidential. Do not disclose or use except as authorized.

end of the first stage. With 14-15 subjects per disease cohort, there is high probability of observing at least one event if a toxicity has an incidence of at least 10%. If the true incidence of an unexpected or severe toxicity is 10% or greater, the probability is at least 0.75 that one or more subjects will experience the toxicity during the early safety monitoring period.

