The distribution of secondary endpoints of PFS and OS will be based on the method of Kaplan-Meier. ORR within each disease cohort will be estimated by the number of subjects with a best response of CR or PR (per RECIST) and presented with exact 90% confidence intervals. For sample sizes of 25 per disease cohort, the confidence intervals will be no wider than 0.35.

Correlative studies will be based on tumor biopsies and will assess changes in biomarkers due to OTT. PD-L1 expression will be classified as positive or negative according to IHC. Pre- versus post-OTT PD-L1 expression will be compared using McNemar's test. Changes in T cell subtypes and in co-stimulatory molecules will be summarized using descriptive methods

CONFIDENTIAL

This document is confidential. Do not disclose or use except as authorized.

TABLE OF CONTENTS

SCHEMA	5
1. OBJECTIVES.....	10
1.1 Study Design.....	10
1.2 Primary Objectives.....	10
1.3 Secondary Objectives.....	10
2. BACKGROUND.....	10
2.1 Study Disease(s).....	10
2.2 IND Agents.....	12
2.3 Rationale.....	33
2.4 Correlative Studies Background.....	34
3. PARTICIPANT SELECTION.....	36
3.1 Inclusion Criteria.....	36
3.2 Exclusion Criteria.....	38
- Note: Subjects with \leq Grade 2 thyroiditis and/or hypophysitis are an exception to this criterion and may qualify for the study.....	39
3.3 Inclusion of Women and Minorities.....	41
4. REGISTRATION PROCEDURES.....	41
4.1 General Guidelines for DF/HCC Institutions.....	41
4.2 Registration Process for DF/HCC Institutions.....	42
5. TREATMENT PLAN.....	42
5.1 Treatment Regimen.....	42
5.2 Pre-Treatment Criteria.....	43
5.3 Agent Administration.....	44
5.4 General Concomitant Medication and Supportive Care Guidelines.....	45
5.5 Criteria for Taking a Participant off Protocol Therapy.....	51
5.6 Duration of Follow Up.....	53
5.7 Criteria for Taking a Participant Off Study.....	54
5.8 Contraception.....	54
6. DOSING DELAYS/DOSE MODIFICATION criteria.....	56
6.1 Pembrolizumab Dose Modifications.....	56
6.2 Dabrafenib + Trametinib Dose Modifications.....	58
7. ADVERSE EVENTS: LIST AND REPORTING REQUIREMENTS.....	74
7.1 Expedited Adverse Event Reporting to the Overall PI and Merck.....	74
7.2 Expedited Reporting to the Food and Drug Administration (FDA).....	75
7.3 Expedited Reporting to Hospital Risk Management.....	75
7.4 Routine Adverse Event Reporting.....	76

CONFIDENTIAL

This document is confidential. Do not disclose or use except as authorized.

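### The 0.35 width bound in Section 13.3 fits a single-stage exact interval; the two-stage 90% interval for CBR exceeds it at every total from 9 to 15 of 25

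*Combined protocol and SAP*

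**What the plan says.** Section 13.3 presents CBR for each cohort with "90% confidence intervals based on the method of Atkinson and Brown, which allows for the two-stage design", and continues: "For samples of size 25, each confidence interval will be no wider than 0.35". The bound is not limited to particular results, so it covers every CBR interval from a cohort that reaches 25 patients.

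The synopsis (Sample Size Justification) places the number differently. For CBR it names the same two-stage method and gives no width. For the objective response rate (ORR) it specifies that results are "presented with exact 90% confidence intervals" and then adds: "For sample sizes of 25 per disease cohort, the confidence intervals will be no wider than 0.35".

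The design is in Section 13.1. Stage 1 has 14 evaluable patients: "If 8 or fewer subjects with clinical benefit are observed, enrollment will stop". With 9 or more, 11 further patients are enrolled, for a total of 25. The decision rule is: "The null hypothesis will be rejected if 16 or more subjects with clinical benefit are observed in 25 subjects".

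**The concern.** An interval that allows for early stopping is not the ordinary binomial interval. Some samples that would have given a low total at 25 patients are cut off at 14, and this changes the tail probabilities from which the limits are found. A width bound worked out for a single sample of 25 need not carry over. The same 0.35 is attached to a single-stage interval in the synopsis and to a two-stage interval in Section 13.3, so one of the two uses is likely to be wrong.

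At stake is the only precision statement the plan makes for its primary estimate. The affected cohorts are those that complete enrolment and fall short of 16 of 25. For them there is no positive test result to report, and the interval is the main summary of what was learned.

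**Working it through.** **Inputs.** From Section 13.1: n1 = 14, stop at 8 or fewer, n2 = 11, n = 25, reject at 16 or more, null CBR 0.50, alternative 0.75. From Section 13.3: 90% level, two-stage method. The documents name the method but do not say how it ranks outcomes that stopped at 14 against outcomes that reached 25. I therefore assumed four usual orderings: stagewise, observed rate S/m, S/√m, and the score (S − 0.5m)/√m, where S is the number with benefit and m is 14 or 25.

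**Step 1: reproduce the plan's design figures.**
- P(stop at stage 1 | 0.50) = P(Bin(14, 0.50) ≤ 8) = 0.788 (plan: 0.79).
- Power at 0.75 = 0.862 (plan: 86%).
- Type I error = 0.086 (plan: at most 0.1).

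**Step 2: reproduce 0.35.** The single-stage exact (Clopper-Pearson) 90% interval at n = 25 is widest at 12 and 13 of 25. At 12 of 25 it is 0.305 to 0.659, width 0.3535, which rounds to 0.35. Wald (0.329) and Wilson (0.312) maxima do not give the stated figure.

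**Step 3: two-stage intervals.** For a total s at 25 patients,

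P(s) = Σ over x = 9 to 14 of Bin(x; 14, p) × Bin(s − x; 11, p),

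and for a stop at stage 1, P(s) = Bin(s; 14, p) with s ≤ 8. The lower limit is the p at which the probability of an outcome ranked at least as high as the observed one equals 0.05. The upper limit is the p at which the probability of one ranked no higher equals 0.05.

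| Total of 25 | 90% width, range over the four orderings |
|---|---|
| 9 | 0.387–0.411 |
| 10 | 0.403–0.411 |
| 11 | 0.402–0.411 |
| 12 | 0.397–0.412 |
| 13 | 0.388–0.406 |
| 14 | 0.373–0.407 |
| 15 | 0.357 (limits 0.444–0.801) |
| 16 | 0.342 (limits 0.471–0.813) |
| 17 | 0.331 (limits 0.503–0.834) |

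The maxima by ordering, in the order listed above, are 0.404, 0.412, 0.411 and 0.412. From 15 of 25 upward the four orderings give identical limits, because 15/25 = 0.600 ranks above every stage 1 stop (at most 8/14 = 0.571) in all of them. Widths keep falling above 17.

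**Step 4: how often this happens.**

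| True CBR | P(finish at 9–15 of 25) | of which exactly 15 | share of cohorts reaching 25 |
|---|---|---|---|
| 0.50 | 12.6% | 4.5% | 59% |
| 0.55 | 15.0% | 6.6% | 44% |
| 0.60 | 14.4% | 7.5% | 30% |
| 0.65 | 11.0% | 6.6% | 17% |
| 0.75 | 2.6% | 1.9% | 3% |

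The last column is the second divided by P(reach 25). At 0.50, for example, 0.126 / (1 − 0.788) = 0.59.

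**The case against.** **The ordering is unknown, so no replacement figure is proven.** This stands in part. Less usual choices move the numbers. Ordering by S − 0.6m gives a maximum of 0.418 and brings 9 of 25 down to 0.325. A score centred on 0.75 gives up to 0.436, at 14 of 25. Mid-p limits bring 15 of 25 down to 0.342. So neither the exact range 9 to 15 nor the value 0.41 is free of assumptions. The failure of the bound does not depend on these choices: totals 10 to 14 exceed 0.35 under every variant tried.

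**Rounding.** The single-stage widths are themselves 0.3515 to 0.3535 at 11 to 14 of 25, so 0.35 is a rounded figure even where it is accepted. On that footing 15 of 25, at 0.357, is a small breach. Leaving it out, the probability of finishing at 9 to 14 is 8.1% at a CBR of 0.50, 6.9% at 0.60 and 0.7% at 0.75. This lowers the frequency, but the excess at the maximum is still 0.05 to 0.06.

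**No decision changes.** True. The rule is a count, the interval is only presented, and whatever the method yields will be reported. This limits the importance of the point; it does not make the sentence correct.

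**The origin of 0.35 is inferred.** Also true. The plan does not say how the figure was obtained. The numerical match and the synopsis ORR sentence make the single-stage calculation the likely source.

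**Conclusion.** The sentence in Section 13.3 is wrong as written. Under the four usual orderings, exact equal-tail two-stage 90% intervals at 25 patients reach 0.404 to 0.412 and exceed 0.35 at every total from 9 to 15. They stay at or below 0.342 for every rejecting total. The error affects the stated precision of the primary estimate in completed cohorts that do not reject the null. Type I error, power, sample size, the stage 1 rule and the 16-of-25 rule are untouched. The assumptions are exact equal-tail limits and an ordering that the documents do not give. The synopsis bound for ORR is correct to the two decimals stated.

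**What to change.** Recompute the widths with the named method, state how it orders outcomes, and replace the sentence in Section 13.3. If the method uses one of the four orderings above, suitable wording is: *With 25 patients, each two-stage 90% interval will be at most about 0.41 wide, and at most 0.35 wide when the null is rejected (16 or more of 25).* If its ordering differs, use the maximum it gives. Leave the ORR sentence in the synopsis as it is.

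Two optional additions:
- A cohort stopped at 14 can have an interval up to about 0.47 wide. The current sentence does not cover that case.
- The count rule governs the decision and the 90% interval is descriptive. At exactly 16 of 25 the null is rejected, yet the interval (0.471 to 0.813) contains 0.50. Reporting the 80% two-stage interval as well would agree with the rule: 0.509 to 0.784 at 16 of 25, and 0.483 to 0.768 at 15 of 25.

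The cost is one sentence, plus one or two more if the additions are wanted. Nothing in the design changes.

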13.4 Analysis of Secondary Endpoints

PFS and OS: The distributions of secondary endpoints of PFS and OS will be based on the method of Kaplan-Meier. Medians of the distributions of PFS and OS will be estimated and presented with 90% confidence intervals based on log(-log(endpoint)) methodology. One-year estimates of OS will also be presented using the same methods.

Early Safety Review: An early, comprehensive safety review will occur at the end of the first stage of the Simon two-stage design and will take place when one cohort has reached the end of its respective first stage according to the Simon design. Since we do not anticipate that adverse events will differ according to BRAF mutation status, all available safety data will be combined from the two cohorts, resulting in an early safety review for up to 28 patients. All reported AEs will be summarized.

For a sample of 28 patients, there is high probability of observing at least one event if a toxicity has an incidence of at least 5%. If the true incidence of an unexpected or severe

toxicity is 5% or greater, the probability is at least 0.75 that one or more patients out of 28 will experience the toxicity during the early safety monitoring period. If the true incidence of unexpected or severe toxicity is 1% or less, the probability is 0.25 or less that at least one patient of 28 will experience the toxicity during the early safety monitoring period. 0 summarizes the probabilities of observing at least one patient with a severe or unexpected toxicity during the initial safety review for a range of true incidence rates.

Table 13.1. Operating Characteristics of Early Safety Monitoring

True Incidence of Unexpected or Severe Toxicity	Probability of Observing One or More Patients with Toxicity among First 28
1%	0.25
3%	0.57
5%	0.76
8%	0.90
9%	0.93
10%	0.95
15%	0.99

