5. TREATMENT PLAN

5.1 Treatment Regimen

Treatment will be administered on an outpatient basis. Expected toxicities and potential risks as well as dose modifications for dabrafenib, trametinib, and pembrolizumab are described in Section 6 (Expected Toxicities and Dosing Delays/Dose Modification). No investigational or commercial agents or therapies other than those described below may be administered with the intent to treat the participant's malignancy.

Response and progression will be assessed at the end of the lead-in phase, and at the start of each 3-week visit thereafter by history and physical exam or in the interim if any new symptoms arise. In addition, radiological imaging (either CT or MRI) will be obtained within 4 weeks of lead-in therapy commencement, within 1 week prior to Week 9, and at 6-week intervals (with a window of -1 week), following the commencement of pembrolizumab for 24 weeks and then extended to 12-week intervals (+2 weeks) while patients remain on the study. Response and progression will be determined based on the Response Evaluation Criteria in Solid Tumors 1.1 (RECIST 1.1). Further, if a patient does not tolerate the combination phase of combination MTT plus pembrolizumab, then MTT will be discontinued and pembrolizumab single-agent phase will begin, presuming that it is safe to treat with pembrolizumab (as outlined in Section 5.3.1).

All patients will be evaluated for anti-tumor activity of the combination. Disease control rate (DCR) at the 24-week time point after commencement of pembrolizumab (in combination with MTT) is the primary anti-tumor end-point. DCR is defined as the percentage of patients per cohort who have stable disease (SD), complete or partial response (CR, PR) without requiring restart of MTT for any reasons. Progression free survival (PFS), CR and PR rates, and overall survival (OS) will also be summarized for patients in each cohort.

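### The 13.6 safety set leaves out patients who stop during the targeted-therapy lead-in; as a minor point, 13.4 gives the early review's sensitivity only for its 28-patient maximum

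*Combined protocol and SAP*

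**What the plan says.** **Safety set.** Section 13.6 defines the safety analysis set by receipt of at least one dose of the drug combination and does not define that term. The same section says that all adverse events recorded in the study will be summarized and that tables will be shown by treatment. Section 7.5 starts adverse event collection at the first dose of study treatment. Section 2.3 has every patient begin with two weeks of MAPK-targeted therapy (MTT) before any pembrolizumab: dabrafenib plus trametinib in cohort 1, trametinib in cohort 2. Section 13.7.1 still carries its template instruction to define who is evaluable, and offers counting from first treatment only as an example.

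**Early safety review.** Section 13.4 says the review "will take place when one cohort has reached the end of its respective first stage according to the Simon design" and that "all available safety data will be combined from the two cohorts, resulting in an early safety review for up to 28 patients". For a toxicity of 5% incidence or more it states that "the probability is at least 0.75 that one or more patients out of 28 will experience the toxicity during the early safety monitoring period". Table 13.1 gives probabilities for 28 patients only. Stage 1 of a cohort is "Fourteen (14) subjects that are evaluable for the primary endpoint" (13.1). The synopsis, under Sample Size Justification, describes the end-of-stage-1 review on a different basis: "With 14-15 subjects per disease cohort, there is high probability of observing at least one event", followed by "If the true incidence of an unexpected or severe toxicity is 10% or greater, the probability is at least 0.75 that one or more" of them will show it.

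**The concern.** A patient who starts targeted therapy, has a toxicity and never reaches pembrolizumab has been treated on study and has reportable events. If 13.6 is followed as written, that patient is outside the analysis set. Lead-in toxicity then either drops out of the tables or appears in a numerator with no matching denominator. Patients who stop early for toxicity are the ones a safety table should not lose, so any bias runs toward a safer-looking regimen.

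For the early review, the question is what a clean result would mean. Someone using 13.4 alone would read it as 0.76 sensitivity at 5% incidence. The trigger is one cohort finishing stage 1, and 2.3 says cohort 1 opens first, with cohort 2 only to be considered later. The review could therefore be held on well under 28 patients.

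**Working it through.** **1. What the drug combination means in 13.6.** Section 13.1 defines primary-endpoint evaluability by a dose of dabrafenib/trametinib/pembrolizumab combination therapy, and describes the early review as a search for severe toxicity of the drug combination. Both point to the study regimen. That list names dabrafenib, which cohort 2 does not receive, so the workable reading is each cohort's MTT plus pembrolizumab.

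**2. Who falls out.** First MTT dose: week 1. First pembrolizumab dose: after the 2-week lead-in (5.3.1). A patient who stops for good in those two weeks is inside the collection window of 7.5 and outside the set of 13.6.

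**3. Effect on a reported rate.** The documents do not say how many such patients to expect, so this is an assumption. Take 14 patients who reach the combination without the event and k who stop in the lead-in with it.

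| k | Event and patient both excluded | Event counted, patient not in denominator | All treated |
|---|---|---|---|
| 1 | 0/14 = 0% | 1/14 = 7.1% | 1/15 = 6.7% |
| 2 | 0/14 = 0% | 2/14 = 14.3% | 2/16 = 12.5% |

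The plan's wording does not settle which column would be reported.

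**4. Table 13.1 reproduced.** The probability of at least one affected patient among n at true incidence q is 1 − (1 − q)^n.

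| q | Stated (n = 28) | Computed, n = 28 | Computed, n = 14 |
|---|---|---|---|
| 1% | 0.25 | 0.2453 | 0.1313 |
| 3% | 0.57 | 0.5738 | 0.3472 |
| 5% | 0.76 | 0.7622 | 0.5123 |
| 8% | 0.90 | 0.9032 | 0.6888 |
| 9% | 0.93 | 0.9287 | 0.7330 |
| 10% | 0.95 | 0.9477 | 0.7712 |
| 15% | 0.99 | 0.9894 | 0.8972 |

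All seven stated values are right for 28 patients.

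**5. The synopsis figure reproduced.** At q = 0.10, n = 14 gives 0.7712 and n = 15 gives 0.7941. Both satisfy the stated minimum of 0.75.

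**6. What the 5% statement needs.** Solving 1 − 0.95^n = 0.75 gives n = ln 0.25 / ln 0.95 = 27.03, so all 28 patients are required. At 5%, n = 20 gives 0.64 and n = 24 gives 0.71.

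**7. Incidence at which 0.75 is reached.** This is q = 1 − 0.25^(1/n): 9.4% for n = 14, 8.8% for n = 15 and 4.8% for n = 28.

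**8. Regimen.** Section 13.4 pools on the expectation that adverse events do not depend on BRAF status, but by 2.3 BRAF status also sets the regimen. For a toxicity specific to the dabrafenib-containing regimen, about 14 to 15 stage 1 patients are informative even in a full pool. That gives 0.51 to 0.54 at 5% incidence.

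**The case against.** *On the safety set.* Section 13.6 also promises to summarize every recorded adverse event, and the early review in 13.4 uses all available safety data, so the 13.6 set does not clearly restrict that review. Lead-in-only patients should be few, since 5.5.1.1 lets even those who progress in the lead-in move on to the combination. This stands as a limit on size. It also answers a stronger inference, that lead-in toxicities would go uncollected or unreported, which the documents do not support. It leaves the denominator unresolved.

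A reader might instead take the combination to mean dabrafenib plus trametinib, as footnote a of the Study Calendar uses the word for cohort 1. That would keep cohort 1 lead-in patients, but it would exclude the whole of cohort 2, so it cannot be what 13.6 intends.

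*On the early review.* Every probability in 13.4 is tied to 28 patients, the pool is openly described as a maximum, and the synopsis gives the per-cohort figure. A reader might infer a miscalculation in Table 13.1, or a contradiction with the synopsis. Neither exists: each statement is correct for its own sample size. What is missing is a statement in 13.4 of what the trigger guarantees.

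A reader might also infer that the review will in fact be held on about 14 patients. The documents do not show this. By 13.1, "A complete safety assessment is planned to coincide with the review of clinical benefit at the end of the first stage", and 5.1 assesses benefit "at the 24-week time point after commencement of pembrolizumab". Cohort 2 could fill during that wait. They give neither cohort's opening date, only that cohort 2 would be considered in mid-2017, so no particular pool size between 14 and 28 can be defended.

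Finally, no decision rule hangs on these probabilities. The data and safety monitoring committee reviews toxicity up to four times a year or more often (12.2), and serious events are reported within 24 hours (7.1). That is why this part is minor.

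**Conclusion.** The safety-set point holds. As written, 13.6 omits patients who stop during the lead-in, while 7.5 and 13.6 itself keep their events. The number affected is unknown and probably small. The conclusion rests on reading the drug combination as MTT plus pembrolizumab, the only reading examined here that works for both cohorts.

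The early-review point holds as a matter of disclosure. Sensitivity at 5% incidence lies between 0.51 (14 patients) and 0.76 (28). What the trigger secures is 0.75 at about 9.4% incidence, which agrees with the synopsis. The 14 are patients evaluable for the primary endpoint, so the number treated may be slightly higher. Neither point touches a stopping rule, the Simon boundaries or the primary analysis.

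**What to change.** 1. In 13.6, define the safety set as all patients who take at least one dose of any study drug, including lead-in MTT. Replace the template text in 13.7.1 with the same definition.
2. In Table 13.1, add an n = 14 column (0.13, 0.35, 0.51, 0.69, 0.73, 0.77 and 0.90 at 1, 3, 5, 8, 9, 10 and 15%) and label n = 28 as the maximum.
3. In the 13.4 text, give the synopsis statement (at least 0.75 at 10% incidence with 14 to 15 patients) as the secured sensitivity. Keep the 5% statement as applying only if all 28 are in the pool.
4. Show the early review by regimen alongside the pooled data, as the by-treatment presentation in 13.6 already implies.

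The cost is wording in three sections, one table column and one extra tabulation. The stated sensitivity becomes less favorable. No patients are added and the pooled review stays.
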